• Arthritis	Non-erosive arthritis involving two or more peripheral joints, characterized by tenderness, swelling, or effusion
• Serositis	a) Pleuritis - convincing history for pleuritic pain or rub heard by a physician or evidence of pleural effusion OR b) Pericarditis – documented by ECG or rub or evidence of pericardial effusions
• Renal disorder	a) Persistent proteinuria greater than 0.5 grams per day or greater than 3+ if quantitation not performed OR b) Cellular casts – may be red cell, hemoglobin, granular, tubular, or mixed
• Neurologic disorder	a) Seizures – in the absence of offending drugs or known metabolic derangements OR b) Psychosis – in the absence of offending drugs or known metabolic derangements
• Hematologic disorder	a) Hemolytic anemia – with reticulocytosis OR b) Leukopenia – less than 4,000/mm ³ total on two or more occasions OR c) Lymphopenia – less than 1,500/ mm ³ on two or more occasions OR d) Thrombocytopenia – less than 100,000 mm ³ in the absence of offending drugs

Criterion	Definition
• Immunologic disorder	a) Anti-DNA: antibody to native DNA in abnormal titer OR b) Anti-Sm: presence of antibody to Sm or nuclear antigen OR c) Positive finding of antiphospholipid antibodies based on (1) abnormal serum level of IgG or IgM anti-cardiolipin antibodies; (2) a positive test result for lupus anticoagulant using a standard method; or (3) a false positive serologic test for syphilis known to be positive for at least 6 months and confirmed by Treponema pallidum immobilization or fluorescent treponemal antibody absorption test
• Antinuclear antibody	An abnormal titer of antinuclear antibody by immunofluorescence or an equivalent assay at any point in time and in the absence of drugs known to be associated with “drug-induced lupus” syndrome

The proposed classification is based on 11 criteria. For the purpose of identifying patients in clinical studies, a person shall be said to have SLE if any 4 or more of the 11 criteria are present, serially or simultaneously, during any interval of observation

16.2 The Systemic Lupus Erythematosus Disease Activity Index 2000 (SLEDAI-2K)

NOVARTIS
CVAY736X2208

Site No.

Subject No.

Date of Assessment

day month year

Visit Number

Page 4001

- ◆ Only record manifestations/items due to SLE Disease Activity occurring in the last 4 weeks
- ◆ TO BE USED IN CONJUNCTION WITH THE SLEDAI 2000 GLOSSARY (Please refer to the following pages)

Descriptor	Weight	Score	Not Present	Not Known
1. Seizure	8			
2. Psychosis	8			
3. Organic brain syndrome	8			
4. Visual disturbance	8			
5. Cranial nerve disorder	8			
6. Lupus headache	8			
7. CVA	8			
8. Vasculitis	8			
9. Arthritis	4			
10. Myositis	4			
11. Urinary casts	4			
12. Hematuria	4			
13. Proteinuria	4			
14. Pyuria	4			
15. Rash	2			
16. Alopecia	2			
17. Mucosal ulcers	2			
18. Pleurisy	2			
19. Pericarditis	2			
20. Low complement	2			
21. Increased DNA binding	2			
22. Fever	1			
23. Thrombocytopenia	1			
24. Leukopenia	1			
TOTAL SCORE				

(Petri et al 2005, Gladman et al 2002)

16.3 British Isles Lupus Activity Group (BILAG) score

BILAG 2004 Scoring Index

 NOVARTIS CVAY736X2208		Page 4001	

 
 
Site No.
 
Subject No.
 
 
 
Date of Assessment
 
 
day
 
month
 
year
 
 
 
		
Visit Number
	

- ◆ Only record manifestations/items due to SLE Disease Activity
- ◆ Score manifestations occurring in the last 4 weeks, as compared with the previous 4 weeks, and based on the principles of the physician's intention to treat
- ◆ TO BE USED IN CONJUNCTION WITH THE BILAG 2004 GLOSSARY

Record: ND Not Done

0 Not present

1 Improving

2 Same

3 Worse

4 New

Yes/No OR Value (where indicated)

CONSTITUTIONAL

- | CONSTITUTIONAL | |
|-------------------------------------|-----|
| 1. Pyrexia - documented > 37.5°C | () |
| 2. Weight loss - unintentional > 5% | () |
| 3. Lymphadenopathy/splenomegaly | () |
| 4. Anorexia | () |

MUCOCUTANEOUS

- | | | |
|--|-----|-----|
| 5. Skin eruption - severe | () | () |
| 6. Skin eruption - mild | () | () |
| 7. Angio-oedema - severe | () | () |
| 8. Angio-oedema - mild | () | () |
| 9. Mucosal ulceration - severe | () | () |
| 10. Mucosal ulceration - mild | () | () |
| 11. Panniculitis/Bullous lupus - severe | () | () |
| 12. Panniculitis/Bullous lupus - mild | () | () |
| 13. Major cutaneous vasculitis/thrombosis | () | () |
| 14. Digital infarcts or nodular vasculitis | () | () |
| 15. Alopecia - severe | () | () |
| 16. Alopecia - mild | () | () |
| 17. Peri-ungual erythema/chilblains | () | () |
| 18. Splinter haemorrhages | () | () |

NEUROPSYCHIATRIC

- | | |
|---|-----|
| 19. Aseptic meningitis | () |
| 20. Cerebral vasculitis | () |
| 21. Demyelinating syndrome | () |
| 22. Myelopathy | () |
| 23. Acute confusional state | () |
| 24. Psychosis | () |
| 25. Acute inflammatory demyelinating polyradiculoneuropathy | () |
| 26. Mononeuropathy (single/multiplex) | () |
| 27. Cranial neuropathy | () |
| 28. Plexopathy | () |
| 29. Polyneuropathy | () |
| 30. Seizure disorder | () |
| 31. Status epilepticus | () |
| 32. Cerebrovascular disease (not due to vasculitis) | () |
| 33. Cognitive dysfunction | () |
| 34. Movement disorder | () |
| 35. Autonomic disorder | () |
| 36. Cerebellar ataxia (isolated) | () |
| 37. Lupus headache - severe unremitting | () |
| 38. Headache from IC hypertension | () |

MUSCULOSKELETAL

- | | | |
|---|-----|-----|
| 39. Myositis - severe | () | () |
| 40. Myositis - mild | () | () |
| 41. Arthritis (severe) | () | () |
| 42. Arthritis (moderate)/Tendonitis/Tenosynovitis | () | () |
| 43. Arthritis (mild)/Arthralgia/Myalgia | () | () |

CARDIORESPIRATORY

- | CARDIORESPIRATORY | | |
|--|-----|-----|
| 44. Myocarditis - mild | () | () |
| 45. Myocarditis/Endocarditis + Cardiac failure | () | () |
| 46. Arrhythmia | () | () |
| 47. New valvular dysfunction | () | () |
| 48. Pleurisy/Pericarditis | () | () |
| 49. Cardiac tamponade | () | () |
| 50. Pleural effusion with dyspnoea | () | () |
| 51. Pulmonary haemorrhage/vasculitis | () | () |
| 52. Interstitial alveolitis/pneumonitis | () | () |
| 53. Shrinking lung syndrome | () | () |
| 54. Aortitis | () | () |
| 55. Coronary vasculitis | () | () |

GASTROINTESTINAL

- | | |
|------------------------------------|-----|
| 56. Lupus peritonitis | () |
| 57. Abdominal serositis or ascites | () |
| 58. Lupus enteritis/colitis | () |
| 59. Malabsorption | () |
| 60. Protein losing enteropathy | () |
| 61. Intestinal pseudo-obstruction | () |
| 62. Lupus hepatitis | () |
| 63. Acute lupus cholecystitis | () |
| 64. Acute lupus pancreatitis | () |

OPHTHALMIC

- | | | |
|---|-----|-----|
| 65. Orbital inflammation/myositis/proptosis | () | () |
| 66. Keratitis - severe | () | () |
| 67. Keratitis - mild | () | () |
| 68. Anterior uveitis | () | () |
| 69. Posterior uveitis/retinal vasculitis - severe | () | () |
| 70. Posterior uveitis/retinal vasculitis - mild | () | () |
| 71. Episcleritis | () | () |
| 72. Scleritis - severe | () | () |
| 73. Scleritis - mild | () | () |
| 74. Retinal/choroidal vaso-occlusive disease | () | () |
| 75. Isolated cotton-wool spots (cytoid bodies) | () | () |
| 76. Optic neuritis | () | () |
| 77. Anterior ischaemic optic neuropathy | () | () |

Ensure that lab values are reported in the correct unit

*Y/N Only select No if value is not due to SLE activity

RENAL

- | Test/Exam | Value () | Due to SLE |
|--------------------------------------|----------------------------|------------|
| 78. Systolic blood pressure (mm Hg) | value () | |
| 79. Diastolic blood pressure (mm Hg) | value () | |
| 80. Accelerated hypertension | Yes/No | |
| 81. Urine dipstick protein | (=1, +=2, +++=3) | |
| 82. Urine albumin-creatinine ratio | mg/mmol | |
| 83. Urine protein-creatinine ratio | mg/mmol | -Y/N* |
| 84. 24 hour urine protein | g/24hrs | |
| 85. Nephrotic syndrome | Yes/No | |
| 86. Creatinine (plasma/serum) | μmol/l () | Y/N* |
| 87. GFR (calculated) | ml/min/1.73 m ² | Y/N* |
| 88. Active urinary sediment | Yes/No | |
| 89. Active nephritis | Yes/No | |

HAEMATOLOGICAL

- | | | | |
|--|---------------|-----|------|
| 90. Haemoglobin (g/dl) | value | () | Y/N* |
| 91. Total white cell count (Gi/L = 10^9 /l) | value | () | Y/N* |
| 92. Neutrophils (Gi/L = 10^9 /l) | value | () | Y/N* |
| 93. Lymphocytes (Gi/L = 10^9 /l) | value | () | Y/N* |
| 94. Platelets (Gi/L = 10^9 /l) | value | () | Y/N* |
| 95. TTP | 0, 1, 2, 3, 4 | | |
| 96. Evidence of active haemolysis | Yes/No | | |
| 97. Coombs Test Positive (Yes/No/Not Required) | | () | |

End of BILAG 2004 Assessment

(Yee et al 2006; Yee et al 2010; Castrejón et al 2014)

Flare determined by BILAG-2004 as below ([Isenberg et al 2005](#); [Isenberg et al 2011](#)):

 CVAY736X2208	

Site No.	Subject No.	

	Site No.	Subject No.	
Page 4001
 

Visit Number	

	Visit Number		
	Site No.	Subject No.					
Visit Number							

Date of Assessment	

day	month	year	

	Date of Assessment			day	month	year	
Date of Assessment							
day	month	year					

BILAG Flare, as defined below, determined by Investigator from BILAG-2004 scores

Ref : ([Isenberg et al 2005](#); [Isenberg et al 2011](#)):

BILAG 2004 Moderate Flare

Two or more B scores, due to items which are 'New' or 'Worse' :

BILAG 2004 Severe Flare

One or more A scores, due to items which are 'New' or 'Worse' :

CCI

A large black rectangular redaction box covers the majority of the page content. On the left side of this box, the letters "CCI" are printed in a large, bold, red font, likely indicating a Confidential Clinical Information watermark.

CCI

CCI

CCI

1.1 Scope of document

The RAP documents contain detailed information to aid the production of Statistics & Programming input into the Clinical Study Report (CSR) for trial “CVAY736X2208”.

The Statistical analysis plan (SAP) describes the implementation of the statistical analysis planned in the protocol for the purpose of the interim analyses and clinical study report.

Tables, Figures, Listings (TFL) details the presentation of the data, including shells of summary tables, figures and listings, and Programming Datasets Specification (PDS) contains programming specifications e.g. for derived variables and derived datasets, to support the creation of CSR outputs.

1.2 Study reference documentation

CCI

1.3 Study objectives

Table 1-1 Objectives and related endpoints

Objective(s)	Endpoint(s)
Primary objective(s)	Endpoint(s) for primary objective(s)

To determine the effect of VAY736 and of CFZ533 versus their respective placebo on disease activity in SLE patients at Week 29 compared to baseline	
SRI-4 response status at Week 29 with reduced steroid dose maintained between Weeks 17 and 29
Secondary objective(s)	Endpoint(s) for secondary objective(s)

To assess safety and tolerability of VAY736 and of CFZ533 in patients with SLE	
Adverse events and other safety data such as vital signs, ECG and laboratory results recorded during study

To determine the change from baseline in the Physicians' Global Assessment (PhGA) at Week 29 in VAY736-, CFZ533- or their respective placebo-treated arms	
Changes between baseline and Week 29 in the PhGA visual analog scale (VAS) assessing patient's overall disease activity

To determine the change from baseline in the Patient's Global Assessment (PGA) at Week 29 in VAY736, CFZ533 or their respective placebo-treated arms	
Changes between baseline and Week 29 in the patients' VAS assessing their global disease activity

To determine the pharmacokinetics (PK) of multiple doses of VAY736 (s.c.) and CFZ533 (i.v.) in SLE patients	
PK Cohort 1 (VAY736): free VAY736 serum concentration (C_{trough}). PK Cohort 2 (CFZ533): free CFZ533 concentration in plasma (C_{max}, C_{trough}).

To assess the effect of VAY736 and of CFZ533 versus their respective placebo to prevent disease flares in SLE patients	
Flare rate and time to first flare, with flare defined as one new 'A' score or two or more 'B' score using BILAG -2004

Objective(s)	Endpoint(s)

To evaluate the immunogenicity of multiple doses of VAY736 (s.c.) or CFZ533 (i.v.) in SLE patients	
Anti-VAY736 (Cohort 1) or anti-CFZ533 (Cohort 2) antibodies and incidence of ADA-positive patients.

To evaluate the pharmacodynamics (PD; rate, extent and duration of target engagement) of multiple doses of CFZ533 in SLE patients	
PD Cohort 2 (CFZ533): total soluble CD40 in plasma

Exploratory objective(s)	Endpoint(s) for exploratory objective(s)
	

Objective(s)	Endpoint(s)
	

1.4 Study design and treatment

This is a randomized, patient- and investigator-blind, placebo-controlled, parallel-group, non-confirmatory study to assess the safety, tolerability, pharmacokinetics, immunogenicity, pharmacodynamics and preliminary clinical efficacy of multiple doses of VAY736 or of CFZ533 in patients with active SLE (see [Figure 1-1](#)).

Figure 1-1 Study design

Key study design features are as follows:

- Patient randomization into one of two treatment cohorts (VAY736 or CFZ533) and to either active or placebo
- Seven-month, placebo-controlled, blinded treatment
- Guided corticosteroids taper from Study Week 5 to Study Week 17
- A 5-month, open label treatment followed by a final outcomes assessment
- Four-month follow up for safety/PK/PD, with additional follow up for VAY736-treated patients until 2 years from end of treatment or B cell recovery criteria are met, whichever occurs earlier

Screening and randomization

The study will randomize approximately 120 patients to test two active treatments against their matching placebo in parallel cohorts. After a 28-day screening period, eligible patients will be enrolled and stratified according to serum extractable nuclear antigens (ENA) status (positive or negative) and baseline SLEDAI-2K score (<10 , ≥ 10). At the baseline visit, patients who are eligible for both cohorts will be randomly assigned to one of the four treatment arms. Patients who are eligible for only one cohort will be randomly assigned to either of the two treatment arms in that cohort. Randomization across the cohorts will be implemented via central randomization aiming for randomization ratio of 1:1:1:1.

Blinded treatment phase

Within the treatment cohort, blinded treatment with the investigational drug (VAY736 or CFZ533) or placebo will be administered on top of patients' stable standard of care therapy for SLE. Visits to assess safety and/or efficacy are scheduled at 4-week intervals. An additional safety visit is scheduled at Week 3 (within the placebo-controlled period) and Week 31 (within the open label period) where patients in Cohort 2 (CFZ533) will receive an additional treatment dose.

On the baseline visit Day 1, following patient eligibility confirmation and completion of all assessments, first dose of study drug/placebo will be administered. The last treatment in the blinded treatment period will be given at the Week 25 visit. The readout for the blinded treatment period will be performed at Week 29. Study drug will be administered every 4 weeks. Unless otherwise stated, all assessments must be completed BEFORE the next dose of study drug is administered.

Guided corticosteroid (CS) reduction

- Patients entering the study on a stable CS regimen are required to undergo a guided CS taper from baseline levels starting at Week 5 in order to achieve by Week 17:
 - a daily CS dose of ≤ 5 mg/day prednisone or equivalent,
 - or a CS dose that is less than the baseline dose, whichever is the lower dose.
- In addition, the patient should remain at the lowered CS dose achieved at Week 17 through to Week 29.
- Patients entering the study without background CS therapy should remain free of any CS regimen or increase in SoC DMARDs through to week 29.

- Patients exceeding the rescue therapy allowances may continue in trial but will be labeled a non-responder for primary endpoint.
- During the open label phase, further reductions in patients' SoC CS and DMARDs may be made on an individual basis as deemed appropriate by the investigator.

Open-label treatment phase

At the end of the Week 29 visit, after all assessments have been performed, the first open label treatment will be administered. Patients in Cohort 1 will receive VAY736 and patients in Cohort 2 will receive CFZ533. Study drug will be administered every 4 weeks. The last treatment will be given at the Week 49 visit, and the End-of-Treatment (EoT) visit will be performed 4 weeks thereafter, at Week 53.

Follow-Up period

After completion of the open-label treatment period, all patients will enter a Follow-Up period in order to monitor safety and efficacy up to Week 69. The Week 69 visit is the End of Study (EoS) visit for patients in Cohort 2 (CFZ533). The study duration for patients in Cohort 2 will be approximately 18 months.

For Cohort 1 (VAY736). Patients who do not achieve B-cell recovery by Week 69 Visit will enter a Secondary Follow-Up period until achieving B cell recovery criteria (B-cell count is at ≥ 50 cells/ μ L or at least 80% of baseline levels). Safety follow-up visits will be scheduled as deemed appropriate until the patient achieves the B cell recovery criteria, followed by an EoS 4 weeks later.

As per protocol amendment 5 and applicable only for the 3 last patients (see [Figure 1-1](#)): Patients who do not achieve B cell recovery by Week 69 Visit will enter into a Secondary Follow-Up period up to 2 years after EoT or until they achieve B cell recovery criteria (B cell count is at ≥ 50 cells/ μ L or at least 80% of baseline level), whichever occurs earlier.

Safety follow-up visits will be scheduled as deemed appropriate until the patient reaches the 2 years after EoT, with or without achieving the B cell recovery criteria, followed by an EoS as soon as practically possible but no more than approximately 4 weeks later.

2 First interpretable results (FIR)

CCI

3 Interim analyses

CCI

4 Statistical methods: Analysis sets

For all analysis sets, subjects will be analyzed according to the study treatment(s) received.

All patients who received at least one dose of any study drug will be included in the safety analysis set.

The PK analysis set will include all patients with at least one available valid (i.e., not flagged for exclusion) PK concentration measurement, who received any study drug and experienced no protocol deviations with relevant impact on PK data.

All patients with evaluable PD parameter data and no major protocol deviations impacting PD data will be included in the PD data analysis “PD population”.

The analysis sets and protocol deviation codes are related as follows:

Table 4-1 Protocol deviation codes and analysis sets

5 Statistical methods: group presentations

The analyses will be performed on Cohort 1 and Cohort 2 separately unless otherwise specified.

For the analysis plan here onwards, treatment groups are defined as below and these groups will be followed for most summary tables by period and treatment group, unless otherwise stated.

- Blinded period (P1, up to and including Visit 190)

Treatment group for blinded period:

- VAY736
- VAY736 Placebo
- CFZ533
- CFZ533 Placebo
- Open label period (P2, from Visit 190 onwards up to EoT) and
- Post-treatment follow-up (P3, starting day after EoT and ends prior to EoS)
- EoS assessment

Treatment sequence for the people participating in the extension:

- VAY736/VAY736,
- VAY736 Placebo/VAY736
- CFZ533/CFZ533
- CFZ533 Placebo/CFZ533

CCI

For long-term VAY736 follow-up (Cohort 1), the descriptive summaries and figures overtime will display all scheduled visits up to the EoS assessment. Patient profiles/ listings will display all available data. The final CSR planned post final DBL will include only VAY736 cohort, as the earlier interim CSR reported the final results for CFZ533 (Cohort 2).

Individual (Spaghetti) plots over time will be performed, unless otherwise stated, by sequence and will include the whole duration of the study.

6 Statistical methods for Pharmacokinetic (PK) parameters

All patients within the PK analysis set will be included in the PK data analysis.

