The sample analysts will receive a copy of the randomization schedule (via request to the Randomization Office), to facilitate analysis of the samples. The sample analysts will provide the sample data to the study team under blinded conditions unless otherwise allowed.

The study statistician will be able to access the randomization list for interim analyses and is allowed to share unblinded information with the rest of the clinical team as appropriate for internal decision purposes, as outlined in [Table 6-4](#). For example, unblinded summaries and unblinded individual data can be shared with the team for interim analyses.

Study programmers and other personnel involved in study data analysis CCI [REDACTED] are allowed to access treatment assignment information for the purpose of conducting interim analyses.

The clinical trial team is allowed to share unblinded results with other sponsor staff (e.g., decision boards) as required for internal decision making on the study or the project at the time of interim analyses while the study is ongoing.

All unblinded personnel will otherwise keep randomization lists and data or information that could unblind other study team members confidential and secure except as described above.

Following final database lock all roles may be considered unblinded.

Table 6-4 Blinding and unblinding plan (up to Study Week 29)

Role	Time or Event			
	Randomi- zation list generated	Treatment allocation & dosing	Safety event (single subject unblinded)	Interim Analysis
Patients	B	B	UI	B
Site staff	B	B	UI	B
Unblinded site staff e.g., pharmacy staff	UI	UI	UI	UI
Drug Supply and Randomization Office	UI	UI	UI	UI
Unblinded sponsor staff e.g., for study treatment re-supply, unblinded monitor(s), sample analyst(s),	UI	UI	UI	UI
Statistician/statistical programmer/ data analysts CCI	B	B	UI	UI
All other sponsor staff not identified above (trial team, project team, management & decision boards, support functions)	B	B	UI	UI

UI: Allowed to be unblinded on individual subject level

B: Remains blinded

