12.1 Analysis sets

For all analysis sets, subjects will be analyzed according to the study treatment(s) received.

The safety analysis set will include all subjects who received any study drug.

The PK analysis set will include all subjects with at least one available valid (i.e., not flagged for exclusion) PK concentration measurement, who received any study drug and with no protocol deviations that impact on PK data.

The primary PD analysis set will include all subjects who received any study drug having no protocol deviations with relevant impact on PD data.

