12.4 Analysis of the primary endpoint(s)

For either investigational drug, the primary analysis will compare active treatment with its matching placebo based on the PD analysis set within either cohort independently.

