7.1 Primary objective

The primary objective is to determine the effect of VAY736 and of CFZ533 versus their respective placebo on disease activity in SLE patients at Week 29 compared to baseline. The primary analysis will compare active treatment with its matching placebo based on the PD analysis set within either cohort independently.

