7.1.1 Variables

The primary endpoint is a composite of SRI-4 response at Week 29 with sustained reduction in oral corticosteroid from Week 17 through Week 29.

SRI-4 response is defined as below:

- having ≥ 4 points reduction from baseline in SLEDAI-2K score AND
- no new BILAG-2004 A organ domain score and no more than one new BILAG-2004 B organ domain scores compared with baseline AND
- < 0.3 mm or < 10 mm point increase if scaled 0 to 3 or 0 to 100 mm, respectively in the physician's global assessment from baseline

Sustained reduction in oral corticosteroids is defined as below:

- ≤ 5 mg/day or \leq baseline dose, whichever is lower, at Week 17
AND
- no increase of that dose from Week 17 through Week 29

When all these criteria are met, the patient is considered as a responder. However, patients receiving CS dosing in addition to the baseline CS dosing levels or subsequent, reduced levels attained at Week 17 after completing the guided corticosteroid tapering period will be considered non-responder for primary endpoint:

- if total daily CS dose is > 30 mg/d prednisone or equivalent, or
- increased daily CS dose is administered > 2 days within a 4-week treatment cycle, or
- daily CS dose is increased within 2 weeks of Study Visit Week 29.

Patients who have taken other rescue medication or prohibited medication (Table 6-3 of study protocol, e.g., new immune suppressive agents or biologics) or drop out before Week 29 will also be considered non-responder for the primary endpoint. Where acute CS administration occurs for purposes other than the treatment of SLE disease activity, patient responder status will be discussed on a case-by-case basis.

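### The primary analysis set can remove patients whom the endpoint scores as non-responders, and no readable text says which rule prevails

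*SAP*

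**What the plan says.** **Set used.** Protocol 12.4 compares active with placebo "based on the PD analysis set within either cohort independently". SAP 7.1 says the same.

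**Protocol definition (12.1).** "The primary PD analysis set will include all subjects who received any study drug having no protocol deviations with relevant impact on PD data". It also states: "For all analysis sets, subjects will be analyzed according to the study treatment(s) received". SAP section 4 repeats the treatment-received rule.

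**SAP definition (section 4).** "All patients with evaluable PD parameter data and no major protocol deviations impacting PD data will be included in the PD data analysis". The readable text does not define evaluable. Table 4-1, which links deviation codes to analysis sets, shows only its title.

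**Endpoint rule (SAP 7.1.1).** Patients who take other rescue or prohibited medication, "or drop out before Week 29 will also be considered non-responder for the primary endpoint". Protocol 12.4.1 scores rescue users as non-responders; its readable text does not mention dropouts. Where acute steroids are given for reasons other than SLE activity, "patient responder status will be discussed on a case-by-case basis".

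**Interim access.** Protocol 6.4 says that "unblinded summaries and unblinded individual data can be shared with the team for interim analyses". Protocol 4.4 places the first interim analysis after about half of the randomised patients have completed Week 29.

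**The concern.** The endpoint turns intercurrent events into an outcome: a patient who drops out or uses prohibited medication has failed. That works only if the patient stays in the denominator. The PD set is defined by conditions that the same events may breach. Use of a medication that Protocol 6.2.3 prohibits can be classed as a deviation affecting efficacy data. A patient who leaves before Week 29 has no Week 29 SLEDAI-2K, BILAG-2004 or physician assessment, and so may be judged not evaluable.

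The order of the two rules is then decisive. If the set is formed first, these patients disappear; if the endpoint is scored first, they count as failures. The documents do not state the order, and the two set definitions differ. The responder difference feeds the posterior criteria that guide decisions in each cohort. Exclusions made after randomisation and related to outcome could therefore move that decision either way.

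**Working it through.** **1. The two rules applied to each type of patient**

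| Patient | Endpoint rule | Protocol PD set | SAP PD set |
|---|---|---|---|
| Drops out before Week 29 | Non-responder (SAP 7.1.1) | In, unless a relevant deviation is recorded | In only if judged evaluable (undefined) |
| Uses a prohibited immunosuppressant or biologic | Non-responder (SAP 7.1.1) | Out if judged a deviation with relevant impact | Out if judged a major deviation impacting PD data |
| Exceeds steroid limits | Non-responder (Protocol 6.2.4 and Table 6-3; SAP 7.1.1) | As above | As above |

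No cell on the right is settled by the readable text.

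**2. The plan's own figures**

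Protocol 12.8.1 assumes 30 per arm, placebo 17% and a true difference of 25 points, so active is 17% + 25% = 42%. It states an 84% chance of meeting the efficacy criteria, and around 10% if there is no difference.

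The criteria (Protocol 12.4.2, SAP 7.1.3) are P(d > 0) > 0.90 and P(d > 0.15) > 0.50, where d is the active minus the placebo responder rate. With x of n responders and a Beta(1,1) prior, the posterior of each rate is Beta(1 + x, 1 + n − x). Summing the binomial probabilities of all (x, y) pairs that meet both criteria gives:

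- 42% v 17%: 81%
- 17% v 17%: 6.0%

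The first criterion alone with a Jeffreys prior gives 82.1% and 10.8%. The prior parameters are not in the readable text, so the stated figures can be neither confirmed nor called wrong. The 81% and 6.0% serve as the baseline below.

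**3. Effect of removing non-responders**

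The documents give no exclusion rate, so the counts are assumptions. Responders are drawn out of 30 per arm. Then a active and b placebo non-responders are removed, and the same criteria are applied to 30 − a and 30 − b patients. The approximate apparent rate in an arm is p × 30/(30 − removed).

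| True rates | Removed, active/placebo | Apparent rates | Apparent difference | Chance of go |
|---|---|---|---|---|
| 17% v 17% | 0/0 | 17.0% v 17.0% | 0 | 6.0% |
| 17% v 17% | 3/3 | 18.9% v 18.9% | 0 | 6.0% |
| 17% v 17% | 6/6 | 21.3% v 21.3% | 0 | 10.3% |
| 17% v 17% | 6/2 | 21.3% v 18.2% | +3.0 points | 11.3% |
| 42% v 17% | 0/0 | 42.0% v 17.0% | 25.0 points | 81% |
| 42% v 17% | 3/3 | 46.7% v 18.9% | 27.8 points | 81% |
| 42% v 17% | 2/6 | 45.0% v 21.3% | 23.8 points | about 70% |

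For the 6/2 row: 0.17 × 30/24 = 0.2125 and 0.17 × 30/28 = 0.1821, a difference of 0.030. For the 2/6 row: 0.42 × 30/28 = 0.450 and 0.17 × 30/24 = 0.2125, a difference of 0.2375.

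Equal removal of 3 per arm leaves the go probability unchanged, although the apparent 25-point difference is inflated. Larger or unequal removal changes the go probability.

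**The case against.** The strongest reply is that the documents give another consequence for these patients. Protocol Table 6-3 designates steroid breaches as non-response and provides for case-by-case withdrawal with other immunosuppressives and biologics. It never mentions exclusion from analysis. Several other sections also label such patients non-responders. The specific rule in SAP 7.1.1 would have little work to do if the general set definition had already removed them. A dropout scored by rule has a determined outcome and can be called evaluable, and Table 4-1 may say exactly that.

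Much of this stands. A reader might infer that the PD set does delete dropouts and prohibited-medication users. The documents do not show that; they show only that the wording allows it. The unreadable table body cannot be held against the plan.

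Three further inferences go too far:

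- **Broken randomisation.** Analysis by treatment received departs from the assigned arm only if a patient receives the wrong treatment, and nothing suggests that this happened.
- **Free discretion over outcomes.** Case-by-case responder status covers only acute steroids given for reasons other than SLE activity.
- **Unblinded adjudication.** The trial team may see unblinded individual data at interim analyses, but no passage says that unblinded staff decide set membership or responder status. Equally, no readable passage requires those decisions to be made blind.

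The size is also open to challenge. The only figure related to dropout is an over-recruitment allowance of about 10% (Protocol 9.1.2), and 10% in each arm is the 3/3 case, where the go probability does not move. That allowance is meant to compensate for early dropouts, which fits poorly with counting them as failures.

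**Conclusion.** The concern holds as an unresolved conflict between two rules, not as a demonstrated exclusion. The primary set is filtered by deviations and analysed by treatment received. The SAP narrows it with an undefined condition that Protocol 12.1 lacks. Nothing readable protects the non-responder rule from being overridden.

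Under assumed unequal removal, the false-go chance goes from 6% to about 11% (6/2), or the chance of a go under a true 25-point effect falls from 81% to about 70% (2/6). With 3 removed per arm neither moves. These figures rest on Beta(1,1) priors, no covariates, 30 per arm and removal of non-responders only. The direction in the actual trial is unknown.

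The study is non-confirmatory and the criteria are a guide, which limits the consequences. They are still the stated basis for decisions on each compound, and the repair is cheap.

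**What to change.** - In Protocol 12.1 and 12.4 and SAP sections 4 and 7.1, define the primary efficacy set as all randomised patients who received at least one dose, analysed in the assigned arm.
- State that dropout, rescue medication and prohibited medication never lead to exclusion and are scored by the non-responder rules of SAP 7.1.1.
- Align the SAP and protocol set definitions. Keep the current PD set as supportive, and report its exclusions by arm with reasons.
- For the case-by-case decisions on steroids given for reasons other than SLE, add a sensitivity analysis that scores all such patients as non-responders. Where still feasible, have these decisions made by staff blinded to arm. This may be too late for Cohort 2, because SAP section 5 says that an earlier interim report already gave its final results.

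The cost is wording, one model re-run per cohort and slightly lower observed response rates. If Table 4-1 already retains these patients, the precedence question needs only one clarifying sentence.
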